9.8.2 Prohibited Therapies

The medications listed in [Table 9-2](#) are prohibited during the study. Balneotherapy is also prohibited during the Screening Period and during the study.

Subjects may not use concomitant keratolytics such as urea, salicylic acid, alpha, or beta hydroxyacids. Subjects may not use topical or systemic retinoids. Subjects may not take more than 3500 IU/day Vitamin A (e.g., as in a multivitamin). Use of benzoyl peroxide is permitted on nontreatment days for subjects with concomitant acne only); it must not be applied on treatment days due to risk of inactivation of trifarotene by benzoyl peroxide.

Subjects receiving excluded therapies will be ineligible for study enrollment or for continued treatment in the study, at the investigator's discretion with consultation with Mayne Pharma LLC and the medical monitor. For enrolled subjects who require prescription of a systemic azole, the principal investigator should discuss with the medical monitor whether the subject may continue in the study.

9.8.3 Restrictions

Subjects should not shower, bathe, or swim for at least 4 hours after study drug application. No occlusive dressings should be applied to areas where study drug was applied.

Subjects should only use investigator-approved emollients and should not use them on treatment days within at least 4 hours before and after study drug application.

In addition, subjects should take protective measures to avoid exposure of treated areas to sunlight, such as applying sunscreen (except within 4 hours before and/or 4 hours after study drug application), and/or wearing protective clothing (e.g., long sleeves, hats, and covering legs and feet), and/or seeking shade or shelter from the sun.

9.9. Treatment after End of Study

After the end of the study, each subject will be treated according to standard clinical practice.

9.10. Dispensing and Storage

The test product supplied by Mayne Pharma LLC is to be used exclusively in the clinical study according to the instructions of this protocol. The investigator is responsible for dispensing the IP according to the dosage scheme and for ensuring proper storage of the IP.

The investigator must confirm the receipt of the IP with his or her signature. A copy of this receipt must be kept by the investigator and another copy will be stored at Premier Research. Until the IP is dispensed to the subjects, it must be stored at 20–25°C (68–77°F), with excursions permitted to 15–30°C (59–86°F); do not freeze and with the tube kept tightly closed in a securely locked area that is not generally accessible.

The key to the storage area is to be kept by the investigator or designee responsible for the IP. The store will be accessible only to those persons authorized by the investigator to dispense the IP.

9.11. Drug Accountability

The investigator must maintain adequate records showing the receipt, dispensing, return, or other disposition of the IPs, including the date, quantity, batch or code number, and identification of subjects (subject number) who received the IP. The investigator will not supply the IP to any person except those named as subinvestigators on the Form Food and Drug Administration (FDA) 1572, designated study personnel, and subjects in this study. The investigator will not dispense the IP from any study sites other than those listed on the Form FDA 1572. Investigational product(s) may not be relabeled or reassigned for use by other subjects. If any of the IP is not dispensed, is lost, stolen, spilled, unusable, or is received in a damaged container, this information must be documented and reported to the sponsor and appropriate regulatory agencies, as required.

Each subject will be given enough tubes of study drug to apply up to 1 tube-full (approximately 36 g of clinical trial material) per treatment day until the next study visit. Tubes will be packed 2 to a carton, and each subject will receive enough cartons to have the maximum number of tubes needed until the next study visit. The number of study drug tubes the subject needs to provide enough IP until the next visit is shown in [Table 9-3](#).

Table 9-3: Amount of Study Drug Needed Per Visit

Treatment Period	Number of Cartons	Number of Tubes
Double-blind Treatment Period		
Baseline	3	6
Day 14	4	8
Day 30	6	12
Day 60	6	12
OLE		
Day 90	3	6
Day 104	4	8
Day 120	6	12
Day 150	6	12

Each carton will be weighed before dispensing (tubes and boxes, but not leaflets) and subjects are to bring all cartons and tubes back at each study visit, whereupon study staff will weigh them again to estimate study drug use and compliance.

Upon completion of the study, the IP (partly used, unused, and empty tubes) must be left in the original packaging and returned to the sponsor or designee for destruction.

9.12. Labeling and Packaging

Labeling and packaging of IP will be performed by Catalent Pharma Solutions.

Tubes will be packaged in cartons comprising 2 tubes each. Tubes will be labeled with inner and outer booklet labels, and carton number. Each carton will also be labeled with inner and outer booklet labels and numbered.

9.12.1 Labeling

The tubes will have a label affixed that meets the applicable regulatory requirements and may include, but is not limited to, the following: subject identifier, IP name, lot number, protocol number, carton number, caution statement, storage, and sponsor identification.

All empty packaging or packaging containing unused tubes should be saved for final disposition by the sponsor or contract pharmacy.

Final labeling will comply with the regulatory requirements of each country where the study will be conducted.

9.12.2 Packaging

Investigational products will be packaged in high-density polyethylene, 35×100 mm tubes weighing 50 g from which a maximum of 36 g of IP can be extracted. Trifarotene cream HE1 and vehicle will be packaged so as to be blinded to the investigator, the study clinic personnel, and the subjects.

10. STUDY PROCEDURES

Subjects must provide written informed consent before any study-related procedures are initiated, including the cessation of prohibited concomitant therapy.

Subjects who agree to participate in the photography and/or PK substudy must provide written informed consent before photographs or serial blood samples are collected.

For the timing of assessments and procedures throughout the study, refer to the Schedule of Events (Section 2.2). Throughout the study, every reasonable effort should be made by study personnel to follow the timing of assessments and procedures in the Schedule of Events for each subject. If a subject misses a study visit for any reason, the visit should be rescheduled as soon as possible.

10.1. Study Duration

10.1.1 Overall Study Schedule

The planned sequence and maximum duration of the study periods for each subject will be as follows:

1. Screening: up to 97 days. Before asking a subject to enter washout, investigators should confirm the subject meets study eligibility criteria, except for LI severity (inclusion criterion #3). Washout may be up to 90 days. After completing any necessary Washout Period, subjects must return to the site within 35 days before the Baseline Visit within the 97-day Screening Period to have their LI severity assessed and study eligibility requirements determined.
2. Double-blind treatment: Twice weekly for 90 days.
3. Optional Open-label Extension treatment: Twice weekly for 90 days.
4. Follow-up: 14 days after last study drug application.

The maximum treatment duration for each subject is approximately 90 days for subjects who choose not to continue into the OLE, and 180 days for those who choose to continue.

The maximum study duration for each subject is approximately 291 days.

10.2. Study Periods and Visits

It is suggested that quality of life assessments be conducted first to avoid any bias, and that the IGA be recorded as the first LI assessment at every visit.

10.2.1 Screening and Washout

10.2.1.1 Screening Visit (Visit 1)

Written informed consent must be obtained before any study-related procedures are performed. Before asking a subject to enter Washout (Section 10.2.1.1.1), investigators should confirm the subject meets study eligibility criteria, except for LI severity (Inclusion Criterion #3). Washout may be up to 90 days. After completing any necessary Washout Period, subjects must return to the

site within 35 days before the Baseline Visit within the 97-day Screening Period to have their LI severity assessed and study eligibility requirements determined.

The following procedures will be performed during Screening:

1. Obtain written informed consent.
2. Assign a screening number when a subject begins screening.
3. Assess inclusion/exclusion criteria.
4. Collect demographic information.
5. Record medical history, including current therapies (e.g., prescription and nonprescription medications).
6. Perform a physical examination.
7. Measure vital signs (systolic blood pressure [SBP], diastolic blood pressure [DBP], and pulse).
8. Measure height, weight, and calculate body mass index (BMI).
9. Record IGA.
10. Record VIIS.
11. Record roughness assessment.
12. Record palm/sole assessment.
13. Record palm/sole assessment of fissuring.
14. Record ectropion score.
15. Perform a 12-lead ECG.
16. Collect blood and urine for laboratory tests, coagulation panel, and serology.
17. Perform serum pregnancy test for WOCBP.
18. Record concomitant medications.

Procedures for rescreening subjects who initially fail to meet study entry criteria are described in Section [14.3](#).

10.2.1.1.1 Washout

Upon signing informed consent and entering the Screening Period, subjects will stop using physical and medical treatments for LI, including balneotherapy, and begin to washout the prohibited topical and systemic treatments with designated washout periods, as applicable ([Table 9-2](#)). Washout may be up to 90 days, as necessary.

After completing any necessary Washout Period, subjects must return to the site within 35 days before the Baseline Visit within the 97-day Screening Period to have their LI severity assessed and to complete any eligibility requirements. During washout, subjects may continue their standard of care of visible skin (face and scalp) for cosmetic reasons and of extremities (palms/soles) to avoid

functional consequences on walking or moving their fingers. In the US/EU, this may include compounded emollients with keratolytics (alpha or beta hydroxyl acids) and/or urea. The investigator should approve and document these standard-of-care treatments in the eCRF. If the standard of care treatments of the face and/or palms/soles contain prohibited medications, they must be stopped at the Baseline Visit. Subjects may shower but not bathe or swim. The IGA will be evaluated on the rest of the body at Baseline.

10.2.2 Double-blind Treatment Period

Eligible subjects who have washed out prohibited medications will be randomized to double-blind study drug.

10.2.2.1 Baseline Visit (Visit 2, Day 1)

The following procedures will be performed on Day 1 in the study clinic:

1. Review inclusion/exclusion criteria.
2. Record responses to DLQI and EQ-5D Quality of Life Questionnaires.
3. Perform a limited physical examination.
4. Record vital signs (blood pressure and pulse).
5. Record concomitant medications and concomitant therapies.
6. Record IGA.
7. Record VIIS.
8. Record roughness assessment.
9. Record palm/sole assessment.
10. Record palm/sole assessment of fissuring.
11. Record ectropion score.
12. At sites where the photographic substudy is conducted, take photographs of subjects who have provided informed consent for the photography.
13. Perform a 12-lead ECG.
14. Perform urine pregnancy test for WOCBP.
15. Collect blood and urine for routine laboratory tests (subject must be fasting; i.e., at least 8 hours) and coagulation panel.
16. Randomize via IWRS.
17. Collect a predose PK blood sample (all subjects).
18. Among subjects who consent to participate in the PK substudy, ensure that PK lines are placed before IP application. The IP will be applied in the clinic at this visit, and samples for PK will be taken at 1, 2, 4, 8, 12, and 24 hours postdose on Day 1.
19. Among subjects in the PK study, perform additional ECGs at times of serial sampling.

20. Clinic staff instructs subject on study drug application, applies initial study drug dose and measures amount used (i.e., study staff will weigh kits (tubes and boxes, but not leaflets) before and after the first application. If the product will be applied at home by someone other than the study subject, it is recommended that this person assist with application at this visit to learn how the IP is applied.
21. Assess and record local tolerance/AEs.
22. Dispense study drug and diaries.
23. Advise subjects regarding permitted emollient(s) for use on nontreatment days; use of emollient(s) and/or sunscreen on study drug treatment days within 4 hours before or after study drug application is prohibited. Remind subjects that at least 24 hours must have elapsed since IP application before their next visit. Subjects should not to apply IP on visit days until after the visit.

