2.2. Schedule of Events

Table 2-1: Schedule of Events for Double-blind Period

	Screening (-97 days to -1 day) Washout up to 90 days ^a	Double-blind Treatment Period						
		Baseline (Day 1)	Telephone Visit (Day 7)	Day 14 ± 5 days	Day 30 ± 7 days	Telephone Visit (Day 45)	Day 60 ± 7 days	Day 90 ^{b,c} ± 7 days (ET)
Visit	1	2		3 ^d	4 ^d		5 ^d	6 ^d
Written informed consent	X							X ^a
Assign screening number	X							
Inclusion/exclusion criteria	X	X						
Demographics	X							
Medical history	X							
Physical examination	X	X ^c						X ^c
Vital signs (blood pressure and pulse)	X	X		X	X		X	X
Height, weight, and BMI	X							X ^b
IGA assessment ^f	X	X		X	X		X	X
VIIS ^g assessment	X	X		X	X		X	X
Roughness assessment ^h	X	X		X	X		X	X
Palm/sole assessment	X	X		X	X		X	X
Palm/sole fissuring assessment ⁱ	X	X		X	X		X	X
Ectropion score	X	X		X	X		X	X
Photographs ^j		X			X			X
Quality of life per Dermatology Life Quality Index (DLQI)		X		X	X		X	X
EQ-5D Quality of Life Questionnaire		X		X	X		X	X

	Screening (-97 days to -1 day) Washout up to 90 days ^a	Double-blind Treatment Period						
		Baseline (Day 1)	Telephone Visit (Day 7)	Day 14 ± 5 days	Day 30 ± 7 days	Telephone Visit (Day 45)	Day 60 ± 7 days	Day 90 ^{b,c} ± 7 days (ET)
Visit	1	2		3^d	4^d		5^d	6^d
12-lead ECG ^k	X	X			X			X
Clinical laboratory tests (hematology, chemistry, urinalysis) ^l	X	X			X			X
Serology (hepatitis B surface antigen, hepatitis C)	X							
Coagulation panel		X			X			X
Pregnancy test for female subjects (serum at Screening; urine subsequently)	X	X			X		X	X
Randomization via IWRS		X						
PK blood sample collection ^m		X		X	X		X	X
Initial study drug application by clinic staff and measurement ⁿ		X						
Application instructions, advice on emollient and sunscreen use		X	X	X	X	X	X	X
Dispense study drug and diaries ^o		X		X	X		X	(X) ^o
Concomitant medications	X	X	X	X	X	X	X	X
Tolerability assessment		X		X	X		X	X
Adverse events (and review diaries)		X	X	X	X	X	X	X
Collect all used/unused study drug ^p				X	X		X	X
Provide information about OLE option					X	X	X	X

Abbreviations: BMI = body mass index; COVID-19 = coronavirus disease 2019; DLQI = Dermatology Life Quality Index; ECG = electrocardiogram; eCRF = electronic case report form; ET = early termination; HEENT = head, eyes, ears, nose, throat; ICF = informed consent form; IGA = Investigator’s Global

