8.2.2 Exclusion Criteria

A subject will be excluded from the study if he or she meets any of the following criteria:

1. Subject has any variant of ichthyosis other than LI or another disorder of keratinization, including syndromic ichthyoses.
2. Subject has current moderate or severe stinging/burning at Screening.
3. Subject has an ongoing cutaneous infection or any other significant concomitant skin disease (other than the LI) which, in the investigator's opinion, may interfere with the study assessments.
4. Subject with fasting triglycerides >200 mg/dL or >2.25 mmol/L and/or total cholesterol >250 mg/dL or >6.5 mmol/L. Subjects whose triglycerides and/or total cholesterol are within normal limits with a stable dose of lipid-lowering agents for at least 6 months may be included.
5. Subject was previously treated with trifarotene/CD5789 in an acne or ichthyosis study.
6. Subject has any other significant concomitant disease, or poorly controlled medical condition other than LI that in the investigator's opinion may put him or her at risk if he or she takes part in the study, and/or that may interfere with the study assessments.
7. Subject has a medical condition that potentially alters bone metabolism (e.g., osteoporosis, thyroid dysfunction, Cushing syndrome, Crohn's disease, or ulcerative colitis). Subjects with hypothyroidism who are on a stable dose of thyroid hormone replacement therapy and whose thyroid-stimulating hormone (TSH) is normal may be included.

8. Subject is being treated for major depression disorder and/or has a history of major depression or suicide attempt requiring hospitalization, medications, and close psychiatric surveillance to prevent suicide attempts.
9. Subject with positive serology for hepatitis B surface antigen, hepatitis C, or are known to be HIV positive or to have AIDS at Screening.
10. Subject with any of the following laboratory values at Screening:
 - a. Aspartate aminotransferase or alanine aminotransferase $>1.5 \times$ upper limit of normal (ULN) defined by the laboratory
 - b. Total bilirubin $>1.25 \times$ ULN at Screening. Subjects with known 1 mg/dL or, in case of Gilbert's syndrome may be included with total bilirubin $>1.25 \times$ ULN
 - c. Hemoglobin <12.5 g/dL for men and <11.5 g/dL for women
 - d. Platelets $<150 \times 10^9/L$ or $>400 \times 10^9/L$.

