9.4. Dose Adjustment Criteria

Local tolerance will be followed very carefully during the study. Subjects will receive information on study drug use and stopping rules and will be instructed to contact the site with any safety/tolerability issues. Study personnel will telephone subjects in between scheduled visits (i.e., at Day 7 and Day 45) to assess safety; an unscheduled clinic visit may be performed, if necessary. During all clinic visits, the investigator will assess local tolerability (stinging/burning, pruritus, or erythema on 0-3 scales [none, mild, moderate, severe]) for each treated body area (chest/abdomen, back, arms, legs, and face/neck), and the following procedures will be followed:

- If a score of 2 (moderate) is recorded for any of the local tolerability assessment scales (stinging/burning, pruritus, or erythema) on any treated area (e.g., the face), the study drug will be applied on this area only once weekly, until the score returns to <2. Continue to treat all other areas twice weekly provided the score is <2 on those areas.
- If a score of 3 (severe) is recorded for any of the local tolerability assessment scales (stinging/burning, pruritus, or erythema) on any treated area, the study drug will not be applied on that area until the score is back to <3 (i.e., “drug holiday”). Continue to treat all other areas twice weekly provided the score is <2 on those areas.

Any changes in dosing must be documented in the subject diary and the eCRF.

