10.3. Assessments

The 5-point IGA is a valid measure of disease severity and meets the need for a clinically meaningful measure of success for ichthyosis studies. The IGA scale was developed with the support of experts from academic reference centers for the treatment of ichthyosis. Each level of severity will consider both the severity of scaling and the severity of roughness (Section 10.3.1.2). While retinoid treatment is expected to reduce scale, it may increase erythema; therefore, in this study, erythema will be evaluated as part of local tolerability.

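### The only Day 1 local tolerability score is listed after the first application and none is scheduled at Screening, so the protocol requires no scored pre-dose value

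*Protocol*

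**What the plan says.** Protocol Section 10.2.2.1 lists the Day 1 procedures. At item 20, "Clinic staff instructs subject on study drug application, applies initial study drug dose and measures amount used". Item 21 is "Assess and record local tolerance/AEs", the only tolerability item that day. The Screening list in Section 10.2.1.1 has 18 items and none scores local tolerability. In Table 2-1 the row "Tolerability assessment" is marked at Baseline and at Days 14, 30, 60 and 90. It is blank at Screening, and the Baseline mark carries no predose or postdose label. Both protocol versions in the document (adults only, and adults with adolescents) have this order and this row.

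Section 13.1 takes the baseline for safety parameters from Visit 1 or Visit 2, following the schedule. For tolerability only Visit 2 is available.

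On what is known before dosing, exclusion criterion 2 in Section 8.2.2 reads "Subject has current moderate or severe stinging/burning at Screening". There is no matching criterion for erythema or pruritus. Section 10.3 makes erythema a tolerability variable: "While retinoid treatment is expected to reduce scale, it may increase erythema; therefore, in this study, erythema will be evaluated as part of local tolerability". Section 9.4 changes application frequency on an absolute score, beginning "If a score of 2 (moderate) is recorded for any of the local tolerability assessment scales (stinging/burning, pruritus, or erythema) on any treated area", and does not refer to the score before treatment.

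**The concern.** Local tolerability is a named safety endpoint, and Section 11.3.1 makes local application site events the adverse events of special interest. The disease can produce the same signs: Section 5.1 lists pruritus among the features of lamellar ichthyosis, and only stinging/burning is restricted at entry. A subject may therefore start with moderate or severe pruritus or erythema.

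To say whether a given subject's reaction is new or worse, a graded value from before the first application is needed. Section 11.1.1 counts a pre-existing condition as an adverse event only if it worsens or changes in character, and Section 13.1.6.2 admits events that began earlier but increased in severity. Both depend on a pre-treatment grade. A score taken just after application would absorb any immediate reaction into the reference. A missing pre-dose score cannot be recovered once the subject has been dosed.

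**Working it through.** The question is one of timing, so the check sets the relevant sections side by side.

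1. **Scheduled scores before treatment.** Screening: 0 (Section 10.2.1.1 and Table 2-1). Day 1: one, listed after application (Section 10.2.2.1, items 20 and 21). Expressly pre-dose: 0.

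2. **Is the Day 1 list a time sequence?** Not strictly. Item 18 says "samples for PK will be taken at 1, 2, 4, 8, 12, and 24 hours postdose on Day 1", and item 19 adds ECGs at the same times, yet the step that "applies initial study drug dose and measures amount used" comes at item 20. Section 9.2 also places the first application after the Baseline measurements, without saying whether tolerability is one of them. List order alone does not prove post-dose scoring.

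3. **What points to post-dose?** There are two things. At Days 14, 30, 60 and 90 (Sections 10.2.2.3, 10.2.2.4, 10.2.2.6 and 10.2.2.7) tolerance comes directly after the efficacy scales or photographs. Only on Day 1 does it sit behind the application. And where a Day 1 procedure must precede dosing, the text can say so: item 17 asks for a predose PK sample. Items 18 and 19 describe a substudy that spans the dose, so their position does not supply a pre-dose tolerability score.

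4. **Result on timing.** Post-dose is the natural reading, and pre-dose is possible but not required. Under either reading the protocol fixes no pre-dose score.

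5. **Extent.** 3 scales (stinging/burning, pruritus, erythema) × 5 areas (chest/abdomen, back, arms, legs, face/neck) = 15 scores per subject. For about 120 subjects, 15 × 120 = 1,800 baseline scores have no required pre-dose timing.

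6. **Where it bears.**
   - Section 9.4 acts at all clinic visits on absolute scores. For a subject who reaches 2 or 3, disease and irritation cannot be told apart by reference to a pre-dose grade.
   - The review in Section 12 that decides on opening Cohort B uses 15 subjects randomized 1:1:1, so 15 / 3 = about 5 per arm. Comparison between arms is weak at that size, and within-subject change would be the natural supplement.
   - In the extension everyone receives 200 µg/g (Section 9.6) and there is no control. Day 90 values carry over as the starting point (Section 10.2.2.7). For former vehicle subjects Day 90 precedes active drug. For the two active arms, at most 120 × 2/3 = 80 subjects, Day 1 is the only visit that could give an untreated graded reference.

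**The case against.** The best defence is that the post-dose timing is inferred from a list that is not chronological. Table 2-1 places the assessment under Baseline, Section 9.2 puts application after the Baseline measurements, and a site could reasonably score first. That stands as far as it goes: the defect is a required timing that is absent, not proof that every site scores late. But a baseline whose timing may vary by site needs the same correction.

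Three stronger readings are tempting and are not supported.

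- A reader might infer that drug irritation cannot be separated from disease at all. At group level through Day 90 it can. Allocation is randomized and double-blind, the vehicle has the same ingredients without CD5789 (Section 9.1), and Section 13.1.6.1 summarizes tolerability by treatment group and visit. Disease-related scores are balanced in expectation.
- A reader might infer that exclusion criterion 2 has nothing behind it. Screening item 3 assesses the entry criteria, so moderate or severe stinging/burning must be judged then, and the criteria are reviewed again on Day 1. What is missing is a recorded 0-3 grade by body area.
- A reader might want to count the subjects who would meet a Section 9.4 threshold on Day 1. The document gives no prevalence of such grades at entry. A grade caused by disease would also meet the threshold whether scored before or after dosing, so such a count would not measure this defect.

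It is also fair that Section 13.1.6.1 plans only descriptive summaries and names no change-from-baseline analysis of tolerability. Section 11.2 treats conditions present at screening as baseline, and medical history, physical examination and, for some subjects, photographs give an ungraded pre-dose reference. Worsening is therefore harder to judge, not impossible.

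**Conclusion.** The point holds in this limited form. The protocol requires no scored pre-dose local tolerability by body area. As listed, the Day 1 score follows the first application; at best its timing is ambiguous. All of the approximately 120 subjects are affected, with 15 scores each.

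The primary efficacy analysis, the randomization, the sample size and the group comparison of active with vehicle through Day 90 are untouched. The loss is in within-subject change, in attributing individual local reactions and Section 9.4 triggers, in the early review of about 5 subjects per arm, and in reading the uncontrolled extension. How much bias a post-dose reference would introduce cannot be stated, because the document gives no figure for immediate reactions to the first application or for grades present at entry. The conclusion rests on the listed procedures and on no assumed rate.

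**What to change.** In Section 10.2.2.1, move the local tolerability scoring (3 scales, 5 areas) ahead of the first application and name it the tolerability baseline. Mark it predose at Baseline in Table 2-1. Record any reaction after the clinic application separately, as an adverse event or as a second score labelled postdose.

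The sponsor should also reconcile how Section 9.4 treats a grade already present before dosing; no rule is proposed here.

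The cost is one reordered item and an eCRF label. No visit is added.
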